10.5 HANDLING PROCEDURES FOR BLOOD SAMPLES FOR PLASMA CONCENTRATION-TIME MEASUREMENTS

Handling procedures for blood samples are presented in the Laboratory Manual.

[figure not shown]
Proprietary confidential information © 2023 Boehringer Ingelheim International GmbH or one or more of its affiliated companies

[figure not shown]
Proprietary confidential information © 2023 Boehringer Ingelheim International GmbH or one or more of its affiliated companies

[figure not shown]

Proprietary confidential information © 2023 Boehringer Ingelheim International GmbH or one or more of its affiliated companies

Proprietary confidential information © 2023 Boehringer Ingelheim International GmbH or one or more of its affiliated companies

10.6 STATISTICAL APPENDIX INCLUDING MODEL PERFORMANCE AND DATA SCENARIOS

The combination BLRMs with overdose control is introduced in [Section 7.1](#) with the prior distributions for the model parameters fully specified. It will be used to guide dose escalation in this study for the BI 836880 plus ezabenlimab combination in the dose-escalation part of this study. Once patients in each cohort have completed the combination MTD evaluation period, the prior distribution will be updated through Gibbs sampling procedures with the accumulated DLT data from the MTD evaluation period. Posterior probabilities for the rate of DLTs will be summarized from BLRM. Selection of the next dose will be based on these probabilities as well as on other safety and laboratory data.

The purpose of this statistical appendix is to evaluate the model behavior and model performance. To evaluate the model behavior, [Section 10.5.1](#) illustrates a series of different scenarios that mimic the ones which might arise during the actual study conduct. On-study recommendations for the next dose combinations by the BLRM with overdose control principle are also provided under various hypothetical outcome scenarios in early cohorts to show how EWOC facilitates on-trial dose-escalation decisions.

10.6.1 Hypothetical data scenarios

These scenarios reflect potential on-study data constellations and related escalation as allowed by the model. It is assumed that each cohort has 3 patients who are all evaluable. At the 1st occurrence of a DLT, additional 3 patients will be added to the current cohort. For each scenario, the probability of overdose for the current dose, as well as the next potential dose and related probabilities of under-dosing, target dosing, and over-dosing are shown (see [Table 10.6.1: 1](#)).

For example, Scenario 1A represents the case that no DLT is observed in the first 2 patients at the starting dose combination of BI 836880 360 mg plus ezabenlimab 240 mg (denoted by 360 mg/240 mg for easier reference). In this case, there are 2 next allowed dose combinations from the model, i.e., 500 mg/240 mg, and 720 mg/240 mg, among which, 720 mg/240 mg has the highest probability of being in the target region. Scenario 1B shows 1 DLT observed in 3 patients at 360mg/240mg, the dose recommended will remain at this level. But if 3 more patients is added to this cohort and number of DLT remains at 1, the next dose allowed will be 500mg/240mg (Scenario 1C).

Scenario 2D: after no DLT observed in 2 patients of 360mg/240mg dose combination, if 2 DLT observed in 6 patients of 500mg/240mg cohort, the dose cannot be escalated further.

Scenario 3A: no DLT in first 3 cohort, the next recommended dose combination will be 1000mg/240mg. If there is 1 DLT out of 3 or 6 patients in 720mg/240mg cohort, the dose recommended will remain at 720mg/240mg as shown in Scenario 3B-3E.

Table 10.6.1: 1 Hypothetical data scenarios

Scenario	Dose comb. BI 836880/ ezabenlimab (mg/mg)	# DLT	# Pat	Current Dose: P(OD)	Next allowed dose comb. (mg/mg)*	Summary of toxicity of next Combination dose		
						P(under dose)	P(target dose)	P(over dose)
1A	360/240	0	2	0.075	500/240 720/240	0.578 0.427	0.312 0.363	0.110 0.210
1B	360/240	1	3	0.226	360/240	0.391	0.384	0.226
1C	360/240	1	6	0.080	500/240	0.461	0.406	0.133
2A	360/240 500/240	0 0	2 3	0.034	720/240	0.551	0.347	0.102
2B	360/240 500/240	0 1	2 3	0.151	500/240	0.434	0.415	0.151
2C	360/240 500/240	0 1	2 6	0.055	720/240	0.392	0.449	0.160
2D	360/240 500/240	0 2	2 6	0.188	500/240	0.313	0.499	0.188
3A	360/240 500/240 720/240	0 0 1	2 3 3	0.139	720/240	0.395	0.466	0.139
3B	360/240 500/240 720/240	0 0 1	2 3 6	0.053	720/240	0.539	0.408	0.053
3C	360/240 500/240 720/240	0 0 2	2 3 6	0.168	720/240	0.289	0.543	0.168
3D	360/240 500/240 720/240	0 1 2	2 6 6	0.222	720/240	0.201	0.577	0.222

The simulations for scenarios and operating characteristics were conducted using R Studio Version 3.2.2 in conjunction with WinBUGS 1.4.3.

10.6.2 Operating characteristics of combination BLRM

Operating characteristics are a way to assess the long-run behavior of a model by illustrating the precision of design in estimating the MTD. Under an assumed true dose-toxicity curve, metrics such as the probability of recommending a dose with true DLT rate in the target interval can be approximated via simulation.

[Table 10.6.2: 1](#) describes 3 assumed true dose-toxicity scenarios which were used to assess the operating characteristics of the combination model. These scenarios reflect a wide range of possible cases as follows:

- Scenario C1: aligned with prior means
- Scenario C2: low-toxicity scenario
- Scenario C3: high-toxicity scenario

Table 10.6.2: 1 Assumed True Dose-Toxicity Scenarios

Scenario C1, P(DLT)	Dose ezabenlimab (mg)	
Dose BI 836880 (mg)	80	240
360	0.138	0.193
500	0.174	0.239
720	0.237	0.334
1000	0.388	0.470
<hr/>		
Scenario C2, P(DLT)	Dose ezabenlimab (mg)	
Dose BI 836880 (mg)	80	240
360	0.07	0.10
500	0.08	0.15
720	0.10	0.20
1000	0.20	0.30
<hr/>		
Scenario C3, P(DLT)	Dose ezabenlimab (mg)	
Dose BI 836880 (mg)	80	240
360	0.20	0.30
500	0.25	0.35
720	0.30	0.45
1000	0.45	0.65

Bold numbers indicate true DLT rates in the target interval (0.16, 0.33).

For each of these scenarios, 1000 trials were simulated. Each cohort consisted of 3 patients and dose escalation complied with the following rules:

- Escalate to the maximal dose combination possible and satisfies the overdose criterion if it is $\leq 300\%$ increase from the current dose.
- If the recommended dose combination satisfying the overdose criterion is $> 300\%$ increase in dose for each compound, then escalate to the highest dose combination which is $\leq 300\%$ increase from the current dose for each compound.
- If any DLT occurs, extra 3 patients will be tested at the current dose combination.

The MTD was considered reached if the following conditions are satisfied:

- The next recommended dose is the same as the current dose;
- At least 1 DLT is observed;
- At least 6 patients have been treated at the MTD dose combination declared by the model;
- At least 9 patients have been evaluated OR the posterior probability of targeted toxicity reaches 50%.

It was then assessed how often a dose was declared as MTD with true DLT rate in the underdose, targeted-, or over-dose range. Furthermore, the average, minimum and maximum number of patients per trial and the average number of DLTs per trial are reported. Results are shown in [Table 10.6.2: 2](#).

Table 10.6.2: 2 Simulated Operating Characteristics

Scenario	% of Trials Declaring an MTD with True DLT Rate in				# Patients	# DLT
	Underdose	Target dose	Overdose	Stopped		
C1: Aligned with prior	33.6	51.9	14.3	0.2	12.75 (6-30)	3.28 (1-12)
C2: Low Tox	50.4	49.6	0	0	15.13 (6-33)	2.209 (1-10)
C3: High Tox	0	91.8	8.2	0	12.74 (6-30)	3.28 (1-12)

In Scenario C1, which reflects the case that the true dose-toxicity is approximately aligned with prior means, almost all of the simulated trials identified the MTD. Approximately 52% of trials were in the target interval and none of them were in the underdose interval. There were 14.3% in the overdose interval and 0.2% of the trials were prematurely stopped either because the MTD was not identified or because the probability of overdose associated with the simulated starting dose had already exceeded the 25% threshold.

Scenario C2 (Low-toxicity scenario) shows similar results with previous Scenario 1 overall. No simulated trials declared a MTD with a true DLT rate in the overdose interval. All of the simulated trials identified the MTD with approximately 50% in the target dose interval and 50% are in the underdose interval, and no trials were prematurely stopped.

Scenario C3 (High-toxicity scenario) illustrates a case with higher-than-expected toxicity. In this case, approximately 92% of the simulated trials identified the MTD within the target interval. Approximately 8% of the simulated trials declared the MTD in the overdose interval, but no trials were prematurely stopped.

By reviewing the metrics presented in [Table 10.6.2: 2](#) it can be seen that the model is not sensitive to different scenarios of true DLT rates. Across three scenarios, the average number of patients participated in dose-escalation ranges from 12.74 to 15.13 and the average number of DLTs observed ranged from 2.209 to 3.28. In general, this model is conservative due to the overdose control criteria. In all scenarios, the probabilities of recommending a dose combination with true $P(\text{DLT}) \geq 33\%$ as MTD are much smaller than probabilities of recommending a dose combination with true $P(\text{DLT})$ between 16% and 33% as MTD.

In summary, the considered data scenarios demonstrate reasonable operating characteristics of the model. On-study recommendations based on the model are consistent with the clinical decision making process, and should be considered in conjunction with other available clinical information by the SMC in deciding the dose combinations to be tested in order to determine the MTD estimates.

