4.1.2 Selection of doses in the trial

4.1.2.1 Part 1

BI 836880 is currently tested as monotherapy in 2 phase I trials. 29 and 24 patients received BI 836880 in trial 1336.1 (every 3 week schedule) and in trial 1336.6 (weekly schedule), respectively. Dose levels between 40 mg and 1000 mg of BI 836880 were tested in the every 3 week trial. Most commonly reported adverse events were hypertension, asthenia, nausea, vomiting, diarrhea and constipation. 5 DLTs occurred in the two studies (pulmonary embolism, proteinuria, hypertension, respiratory distress). Other relevant adverse events (mode of action related) include peripheral edema and bleeding (epistaxis).

Based on safety data as well as PK and PD analysis, the dose of 720 mg is selected as recommended phase 2 dose (RP2D). This dose will be the highest dose that can be tested in combination with ezabenlimab. The dose below this dose tested in monotherapy trial (360 mg) is safe and showed complete inhibition of systemic targets, and will be used as starting dose for the combination with ezabenlimab. However because of the important safety difference between 360 and 720 mg (mainly occurrence and severity of hypertension), a BI 836880 intermediate dose of 500 mg will be tested. The highest tested dose levels will be expanded before selection of BI 836880 dose to be used for Part 2 of the trial.

In the monotherapy phase I trial (1381.1), a total of 9 patients received ezabenlimab at 3 dose levels (80 mg, 240 mg and 400 mg) in the dose escalation cohorts. There were no DLTs or drug-related SAE reported in any cohort. The most common reported AEs were nausea, fatigue, decreased appetite, constipation and arthralgia. Eight additional patients have been treated at dose of 240 mg in the expansion part of this trial. No grade 4, Grade 5 AE or DLT was reported.

The exploratory analysis of biomarker performed in these 9 patients shows 100% PD-1 receptor occupancy in peripheral blood in all on-treatment patient samples compared to baseline throughout one treatment cycle.

Plasma concentration of ezabenlimab appears to increase linearly (based on AUC0-504h Cmax and Cpre). Furthermore, the observed ezabenlimab PK was compared with model simulated pembrolizumab PK ([R17-2460](#)). Observed ezabenlimab PK profiles overlap with those simulated for pembrolizumab at a dose of 200 mg.

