Since a Bayesian approach is applied, prior distributions f for each of the parameter vectors $\theta_1 = (\log(\alpha_1), \log(\beta_1))$, $\theta_2 = (\log(\alpha_2), \log(\beta_2))$ and for the interaction term η need to be specified. The prior distributions for θ_1 and θ_2 will be specified as mixtures of two multivariate normal distributions, i.e.

$$a(\theta_k) = a_{1,k} f_1(\theta_k) + a_{2,k} f_2(\theta_k)$$

with

$a_{1,k}, a_{2,k}$ the prior mixture weights, $k=1,2$ and

$$f_i(\theta_k) = \text{MVN}(\mu_{ik}, \Sigma_{ik}) \quad (k=1,2),$$

the multivariate normal distribution of the i -th component with mean vector μ_{ik} and covariance matrix Σ_{ik} , where

$$\Sigma_{ik} = \begin{pmatrix} \sigma_{ik,11}^2 & \sigma_{ik,11}\sigma_{ik,22}\rho_{ik} \\ \sigma_{ik,11}\sigma_{ik,22}\rho_{ik} & \sigma_{ik,22}^2 \end{pmatrix}$$

Mixture prior distributions have the advantage that they allow for specification of different logistic dose-toxicity curves, therefore making the prior more robust.

A weakly informative normal prior distribution will be used for η .

The estimated probability $\pi_{12,d1,d2}$ of a DLT at each dose combination d_1, d_2 from the model will be summarized using the following intervals:

Under dosing: [0.00, 0.16)

Targeted toxicity: [0.16, 0.33)

Over dosing: [0.33, 1.00]

The BLRM-recommended dose combination for the next cohort is the level with the highest posterior probability of the DLT rate falling in the target interval [0.16, 0.33) among the dose combinations fulfilling the EWOC principle. Per EWOC it should be unlikely (i.e., <25% posterior probability) that the DLT rate at the dose combination will exceed 0.33. However, the maximum allowable dose increment for the subsequent cohort will be no more than 100% for each compound.

The MTD may be considered reached if one of the following criteria is fulfilled:

1. The posterior probability of the true DLT rate in the target interval [0.16, 0.33) of the MTD is above 50%, OR
2. At least 8 patients have been treated in the study, of which at least 6 at the MTD.

Prior derivation:

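### The Part 1 simulations use escalation and MTD rules that differ from the protocol's, and the 0% stopping reported under high toxicity cannot arise from the stated model

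*Protocol*

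**What the plan says.** Section 7.1.1.1 sets the rules for Part 1.

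- Overdose control: "Per EWOC it should be unlikely (i.e., <25% posterior probability) that the DLT rate at the dose combination will exceed 0.33".
- Dose choice: among combinations that meet this limit, the one with the highest posterior probability in the target interval 0.16 to 0.33.
- Increment: "the maximum allowable dose increment for the subsequent cohort will be no more than 100% for each compound".
- MTD: either a target-interval probability above 50%, or "At least 8 patients have been treated in the study, of which at least 6 at the MTD". No DLT is required.

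Section 4.1.2.1 says of 720 mg BI 836880: "This dose will be the highest dose that can be tested in combination with ezabenlimab". Section 3.1 starts the escalation at 360 mg with 240 mg ezabenlimab.

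Section 10.6.2 simulates 1000 trials per scenario under other rules.

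- Dose choice: "Escalate to the maximal dose combination possible and satisfies the overdose criterion", with increments up to 300%.
- Cohorts: 3 patients, and 3 more at the same dose after any DLT.
- MTD: four conditions that must all hold. The same dose is recommended next; at least 1 DLT has been seen; at least 6 patients were treated at that dose; and "At least 9 patients have been evaluated OR the posterior probability of targeted toxicity reaches 50" per cent.
- Grid: 360, 500, 720 and 1000 mg, each with 80 or 240 mg ezabenlimab.

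For C3, Table 10.6.2: 2 reports 91.8% on target, 8.2% overdose and 0 stopped; the text repeats: "Approximately 8% of the simulated trials declared the MTD in the overdose interval, but no trials were prematurely stopped". For C1 it reports 0.2% stopped, and the text gives as a reason for stopping that the overdose probability at the starting dose exceeded 25%. Section 7.1.1.2 concludes from these assessments that the model behaved very well.

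**The concern.** Operating characteristics support a design only if they were simulated under that design's rules. Here the dose choice, the increment limit, the MTD definition and the dose range all differ from the protocol's.

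The stopping column is also implausible on its face. In C3 the true DLT rate at the starting combination is 0.30, close to the overdose boundary of 0.33, and the rule stops the trial once no combination has an overdose probability below 25%. A run of early DLTs should then end a good share of trials.

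At stake is the evidence the protocol offers for its escalation rule: a 91.8% on-target rate with no stopping when toxicity is higher than expected.

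**Working it through.** **1. Reproducing the plan's own figures.** The model was rebuilt from the equations in Section 7.1.1.1 and the priors in Table 7.1.1.1: 3 (1,000,000 prior draws, weighted by the binomial likelihood). Overdose probabilities:

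| Case | Rebuilt | Table 10.6.1: 1 |
|---|---|---|
| 1A, next dose 720/240 | 0.210 | 0.210 |
| 1B, 360/240 after 1/3 | 0.224 | 0.226 |
| 1C, 500/240 after 1/6 | 0.132 | 0.133 |
| 3D, 720/240 | 0.221 | 0.222 |

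The prior overdose probabilities in Table 7.1.1.1: 4 come out within 0.01. The rebuilt model is therefore the protocol's model.

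**2. When the trial must stop.** Posterior overdose probability after DLTs at the 360/240 start:

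| Data at 360/240 | 360/80 | 500/80 | 360/240 |
|---|---|---|---|
| 3/6 | 0.39 | 0.48 | 0.54 |
| 2/3 | 0.40 | 0.47 | 0.57 |
| 3/3 | 0.57 | 0.62 | 0.91 |

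The other five combinations are worse than 360/80 in every row. So after 3/6 nothing on the grid meets the 25% limit. More than 3 DLTs in 6 is worse still.

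**3. A floor on the stopping rate.** Three patients are treated, and three more if any of the first three has a DLT. With true rate p at the start,

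P(at least 3 of 6, at least 1 in the first 3) = P(Bin(6, p) ≥ 3) − (1 − p)³p³.

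- C3, p = 0.30: 0.2557 − 0.343 × 0.027 = 0.2464. Reported: 0%.
- C1, p = 0.193: 0.0905 − 0.5256 × 0.0072 = 0.0867. Reported: 0.2%.
- C3 from a 360/80 start, p = 0.20: 0.0989 − 0.512 × 0.008 = 0.0948. After 3/6 there, the overdose probability is 0.50 at 360/80, the lowest on the grid.

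The chance of no stop in 1000 trials is (1 − 0.2464)^1000, about 1e-123, or about 6e-44 from the 360/80 start. Counting only 3/3 in the first cohort (0.30³ = 0.027, or 0.20³ = 0.008), it is still about 1e-12 or 3e-4.

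**4. Full simulation of C3, 1000 trials per reading.** What a maximal dose means in two dimensions is not defined, so several readings were run.

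| Rules | Start | Stopped | Target | Overdose |
|---|---|---|---|---|
| 10.6.2, highest dose | 360/240 | 46.2% | 33.1% | 20.5% |
| 10.6.2, highest target probability | 360/240 | 40.3% | 48.6% | 11.1% |
| 10.6.2, highest dose | 360/80 | 31.7% | 52.2% | 16.0% |
| 10.6.2, highest target probability | 360/80 | 26.7% | 61.2% | 12.1% |
| 10.6.2, highest dose, 240 mg ezabenlimab only | 360/240 | 73.7% | 2.7% | 23.6% |
| 7.1.1.1, full grid | 360/240 | 38.7% | 52.0% | 9.3% |
| 7.1.1.1, 360 to 720 mg with 240 mg only | 360/240 | 66.3% | 7.2% | 26.5% |
| Table 10.6.2: 2 | not stated | 0% | 91.8% | 8.2% |

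No reading comes near the reported row.

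**5. Other signs in the same table.**

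- C1 and C3 show the same DLT summary, 3.28 (1-12), and nearly the same mean size, 12.75 and 12.74, although every C3 rate is higher than its C1 counterpart.
- The text on C1 says no trial declared an underdosed MTD; the table says 33.6%.
- The C1 true rates (0.138, 0.193, up to 0.470), described as aligned with prior means, are the prior overdose probabilities in Table 7.1.1.1: 4. The means there are 0.174, 0.214, up to 0.363.

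**6. How the two MTD rules diverge.** With 0/2 at 360/240 and 0/6 at 720/240, the second criterion of Section 7.1.1.1 is met (8 treated, 6 at the dose). The target probability at 720/240 is then 0.24. The simulated rule cannot declare an MTD on these data, because there is no DLT.

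**The case against.** Several points on the other side have weight.

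- The 300% limit changes little at the first step. After 0/3 at 360/240 the overdose probability at 1000/240 is 0.34 and at 1000/80 is 0.27, so overdose control already blocks the jump. This stands. The wider limit matters mainly for going back from 80 to 240 mg ezabenlimab (+200%).
- The rule mismatch does not explain the missing stops: on the full grid from 360/240, C3 stopping is about 40 to 46% under the appendix rules and 39% under Section 7.1.1.1. This stands; they are two separate faults.
- The appendix's explicit safety claim is that overdosed MTDs are much rarer than on-target ones. On the full grid under Section 7.1.1.1 that survives (9.3% against 52.0%), and more stopping is more protective. It fails for C3 when ezabenlimab stays at 240 mg with BI 836880 up to 720 mg (26.5% against 7.2%).
- Ending at 720 mg after 0/6 is sensible, since 720 mg is the cap and the overdose probability there is 0.02. Fair: the example shows that the rules differ, not that the protocol's rule is wrong.
- Section 10.6.2 does not state its starting dose. True, but the alternative 360/80 start still gives a floor of 9.5%.
- The prior is labelled illustrative. It is nevertheless the prior that reproduces the appendix's data scenarios.
- Part 1 is finished, and the SMC has chosen 720/240. This limits the consequence but does not make the table right.

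**Conclusion.** The concern holds. The operating characteristics in Section 10.6.2 were produced under rules and a dose range other than those the trial was to follow, and the C3 row is incompatible with the stated prior, grid and 25% limit. At least 24.6% of C3 trials must stop from the 360/240 start (9.5% from 360/80), against 0% reported; simulation gives 27 to 74% under the appendix rules, depending on the reading. The C1 figure is also too low: a floor of 8.7% against 0.2%. With at least 24.6% stopped, at most 75.4% of C3 trials could declare any MTD, so 91.8% on target is not attainable from that start.

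This rests on the printed grid of eight combinations, the priors of Table 7.1.1.1: 3, and stopping whenever no combination meets the overdose limit. A 0% could arise only if the simulation ignored that limit at the lowest dose or used doses not listed; either would itself need correcting. What is affected is the stated justification of the escalation design. No pending dose decision depends on it.

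**What to change.** Choose one set of rules for increments, dose choice, cohort expansion and MTD declaration, and state it identically in Sections 7.1.1.1 and 10.6.2. State the simulated starting dose and what a maximal combination means. Re-run C1 to C3 under those rules with BI 836880 limited to 720 mg, counting a stop whenever no combination has an overdose probability below 25%. If C1 is meant to follow the prior means, take its rates from the mean column of Table 7.1.1.1: 4. Replace Table 10.6.2: 2 and its text, including the C3 row and the C1 underdose statement, and revise the conclusion in Section 7.1.1.2 to match.

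The cost is one simulation re-run and an edit to the appendix. The C3 on-target rate will fall and a real stopping rate will appear. With Part 1 complete, the correction can be made in the next amendment or documented with the trial report.

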10.7 APPENDIX - PERFORMANCE STATUS CRITERIA

ECOG Performance Status Scale		Karnofsky Performance Scale	
Grade	Descriptions	Percent	Description
0	Normal activity. Fully active, able to carry on all pre-disease performance without restriction.	100	Normal, no complaints, no evidence of disease.
		90	Able to carry on normal activity; minor signs or symptoms of disease.
1	Symptoms, but ambulatory. Restricted in physically strenuous activity, but ambulatory and able to carry out work of a light or sedentary nature (e.g., light housework, office work).	80	Normal activity with effort; some signs or symptoms of disease.
		70	Cares for self, unable to carry on normal activity or to do active work.
2	In bed <50% of the time. Ambulatory and capable of all self-care, but unable to carry out any work activities. Up and about more than 50% of waking hours.	60	Requires occasional assistance, but is able to care for most of his/her needs.
		50	Requires considerable assistance and frequent medical care.

ECOG Performance Status Scale		Karnofsky Performance Scale	
3	In bed >50% of the time. Capable of only limited self-care, confined to bed or chair more than 50% of waking hours.	40	Disabled, requires special care and assistance.
		30	Severely disabled, hospitalization indicated. Death not imminent.
4	100% bedridden. Completely disabled. Cannot carry on any self-care. Totally confined to bed or chair.	20	Very sick, hospitalization indicated. Death not imminent.
		10	Moribund, fatal processes progressing rapidly.
5	Dead.	0	Dead.

